Participation in the pilot and main parts for the study is completely voluntary, and there will be no pressure or time constraints regarding the decision to participate. If subjects experience headaches, they can withdraw without any ramifications pertaining to their respective clinic. There are no benefits to the participants except for the compensation, as well as the good will of helping the progress of scientific research. The information learned from this study may aid our understanding of the role of the TMS in modulating cognition and brain function in patients HIV and tobacco use disorder.

#### Available Alternative Opportunities/Treatments

Describe alternative treatments or opportunities that might be available to those who choose not to participate in the study, and which offer the subject equal or greater advantages. If applicable, this should include a discussion of the current standard of care treatment(s).

There are no alternative treatments suggested in this study

[Back to Top](#)

#### Records, Privacy, and Confidentiality

Specify where the data and/or specimens will be stored and how the researcher will ensure the privacy and confidentiality of both. Specify who will have access to the data/specimens and why they need access.

Describe how data will be managed after the study is complete:

- If data/specimens will be maintained, specify whether identifiers will be removed from the maintained information/material.
- If identifiers will not be removed, provide justification for retaining them and describe how you will protect confidentiality.
- If the data/specimens will be destroyed, verify that this will not violate [retention policies](#) and will adhere to applicable facility requirements.

If this study will use de-identified data from another source, describe what measures will be taken to ensure that subject identifiers are not given to the investigator.

If applicable, describe procedures for sharing data/specimens with collaborators not affiliated with UK.

For additional considerations:

[Return of Research Results or Incidental Research Findings](#)

[HIPAA policies](#)

[FERPA policies](#)

[Procedures for Transfer agreements](#)

[Information regarding multi-site studies](#)

[NIH Genomic Data Sharing \(GDS\) Policy](#)

## Digital Data

Personal information of participants (Subjects' age, comorbid medical or psychiatric illnesses, history of substance use, history of traumatic brain injury/loss of consciousness, previous adverse effects with TMS, medication history, duration of treatment with suboxone, urine drug screens, breathalyzer test results) will be stored in an excel sheet on a protected laptop at [name] (In a locked office and behind a protected firewall). The excel sheets containing the personal information will be saved as an encrypted file every time. A data crosswalk of patient/participant name and MRN will be stored separately from deidentified data and any other research data. Any data sharing will be restricted to the de-identified data. Data will be kept for a minimum of 7 years, and electronically destroyed by UK Policy A13-050 and UK Policy A05-055. For the study proper, urine samples will be collected prior to every TMS session to perform drug screening.

Participant data will be stored in an excel sheet on a protected laptop at [name] (In a locked office and behind a protected firewall). The excel sheet containing personal information will be saved as an encrypted file every time new data is entered. A data crosswalk of patient/participant name and MRN will be stored separately from the deidentified data. Any data sharing will be restricted to the de-identified data. Data will be kept for a minimum of 7 years, and electronically destroyed by UK Policy A13-050 and UK Policy A05-055. Urine samples will be collected prior to every TMS session to perform drug screening.

Before recruitment of a subject into the study we will phone screen the subject for seizure disorder, as part of recruitment. We will also screen for previous adverse effects to TMS. Prior to the MRI session, we will also screen for metallic implants/devices in the body. This will also be clarified with the subject.

Should a participant voice suicidal ideation at any point during the study, a thorough risk assessment would be completed immediately and the appropriate resources would be contacted including emergency and/or outpatient resources. To mitigate risk of breach of confidentiality or invasion of privacy, all procedures as part of the study will be completed at [name] offices. Participant personal information and medical/psychiatric history will be stored on the University of Kentucky building at [name]. Also, in order to mitigate risk of breach of confidentiality or invasion of privacy, HIPAA will be discussed with each participant at each session.

The main risks with TMS include seizures. We will screen subjects for known risk factors for seizure with rTMS (medical screening and medical history). Personnel who administer rTMS are trained to recognize a potential seizure event and to act as "first responders" to administer appropriate initial care. All study personnel will undergo basic life skills (BLS) training, and seizure-specific training. The major physical signs the study personnel will look out for in detecting a potential seizure include chewing movements, convulsions/tremor/shaking, difficulty talking, a blank stare, eyes rolling up, and profuse sweating. If any of these signs are observed, study personnel will stop the research procedure and inquire whether the subject feels okay. If the subject is unresponsive (and therefore likely experiencing a seizure), first-aid will be supplied. The first-aid response consists of making sure the subject is physically safe for the duration of the seizure. This involves moving the subjects out of the TMS chair and onto the floor lying down on his or her left side. The subject will be kept lying down on his or her left side, while the staff call emergency medical help, via a 911 call. Resources available in the laboratory include a first-aid kit and immediate phone access. A seizure constitutes a reportable adverse event, and will thus be immediately reported to the IRB via the Safety Events Form mechanism.

Initial measures for syncope are identical to those for seizures. TMS will be terminated immediately, and the subject assisted in controlled reclining without impact. Airway breathing and circulation will be assessed. Unless tonic-clonic seizure activity occurs, the subject will be turned on one side to help clear the airway and avoid aspiration.

An MRI procedure is considered to be "minimal risk" according to federal definitions. To date, no after effects have been revealed and the FDA has classified the MR procedure as possessing a "non significant risk" for the subject of study. To minimize risks, all subjects will be screened for metallic devices, implants and other contraindications to scanning. Women of child-bearing capacity will be evaluated for pregnancy using a urine pregnancy test prior to scanning. Those unlikely to tolerate the sense of confinement during scanning will also be excluded. Adequate safety monitoring and observation during scanning will be provided, as will measures to enhance the subject's physical and emotional comfort during the scan. It is possible that some subjects might experience minor distress by the confined and noisy conditions in the scanner. This possibility will be minimized by earplugs and headphones, and experienced technicians who will monitor all subjects for distress. In the event that a subject becomes anxious during a scan, the study will be halted. Subjects will be able to communicate with the investigators at all times using the intercom system should they wish to request that a study be terminated or have concerns or questions during the procedure. The subject is in full view of the operator at all times. The probability of an incidental finding that might lead to the diagnosis of an unknown abnormality is greater than zero. To identify if there are any incidental abnormalities, all scans obtained in this study will be reviewed by the principal investigator [name] who is a board certified psychiatrist. He has experience with reviewing brain MRI scans as part of previous research studies and in his clinical experience. All subjects will be alerted to this possibility during the consent process. In that event, subjects or their designated physician will be provided copies of their anatomical scans and advised to seek further evaluation if they have concerns. Subjects will be transported between [name] and MRISC using UberHealth ([www.uberhealth.com](http://www.uberhealth.com)) operated and maintained by Department of Psychiatry.

Subjects will be transported between [name] and MRISC using UberHealth. The risk associated with transportation do not exceed any risk associated with vehicle transportation in everyday life.

If subjects experience headaches they can withdraw without any ramifications pertaining to their respective clinic (Bluegrass/SMART/Beyond Birth). If subjects are hurt or get sick because of something that is done in this study, they can immediately call [name] at [name]. After business hours, they can call the Psychiatry department On Call Group at [contact] and explain to the physician that you are a study participant. The physician will determine what type of treatment, if any, is best for you at that time. The medical costs related to care and treatment because of research related harm will be their responsibility. The University of Kentucky Medical Center has no way to provide compensation for research subjects who receive injuries as a result of participating in biomedical and behavioral research. This means that while all investigators will do everything possible in providing careful medical care and safeguards in conducting this research, there is no way in which the institution can pay for the unlikely

occurrence of injury resulting solely from the research itself.

**UK IRB policies** state that IRB-related research records must be retained for a minimum of 6 years after study closure.  
 Check this item to confirm that you will retain all IRB-related records for a minimum of 6 years after study closure.

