On day one of the study, following informed consent, we will perform baseline assessments including breath alcohol level, opioid and tobacco craving questionnaires, smoking attentional bias tasks using eye tracker, inhibitory control and delay discounting tasks, collection of baseline demographics, vital signs (including heart rate, systolic and diastolic blood pressures), Snaith Hamilton Pleasure Scale and Hamilton depression rating scale. All of these baseline assessments will take a total of three hours. We will also obtain resting and active motor threshold from the first dorsal interosseous (FDI) muscle. Following this subjects will be transported to Magnetic Resonance Imaging and Spectroscopy Center (MRISC), affiliated with University of Kentucky for collection of their baseline MRI brain scan that will last thirty minutes. Subjects will also be escorted to the MRISC at the UK Medical Center by the PI ([name]) and a research assistant. Subsequently, neuroimaging data (MRI brain) will be acquired using a Siemens 3-Tesla (3T) PRISMA MRI scanner as described under Data Collection below. On the second and third days, subjects will receive either four sessions of active TBS or four sessions of sham stimulation. Subjects will receive all four sessions of either TBS or sham on one particular day, all four sessions will be the same in dosing and will be delivered at an interval of fifty minutes each. Each session will last ten minutes regardless of it being TBS or sham. Sessions will be delivered 120% resting motor threshold (RMT) to the left dorsolateral prefrontal cortex using a figure 8 coil and MagVenture MagPro x100 device (MagVenture A/S, Denmark), with TMS coil position stabilized using BrainSight (Rogue Solutions, Montreal, Canada). Deciding who will get TBS/sham sessions on day two will be done in a randomized manner with counterbalancing. Along with the stimulation, subjects will also perform a host of other tasks as shown in figures 1. Craving for cigarettes will be measured while performing a stress induction procedure involving immersion of feet in cold water coupled with performing a working memory task (cold pressor test and PASAT as described below). The figures also indicate the timing of these tasks. At the end of the stimulation sessions and tasks, post session MRI brain scans will be collected and subjects will be dispersed payments for the respective days.

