On day two of the study will be the TMS session. We have two groups in this study, and you may be assigned to the actual TMS group or placebo by chance. If you are assigned to the actual TMS group, you will receive the intended experimental method of stimulation and dosing. The TMS paradigm we use is called theta burst stimulation (TBS) which is short and efficient TMS stimulation method. In this group, you will receive four sessions of actual TBS. In the placebo group, you will receive a different kind of stimulation which mimics the actual experimental one but does not deliver any electricity to the brain. This is called sham TMS and you will receive four sessions of it. In both groups, sessions will be separated by 50 minutes and during this time, you will perform a visual attention and a few scales to measure your craving for opioids and cigarettes. On day two we will also have you perform a stress test to assess craving for opioids and cigarettes. This would involve immersing your feet in cold water for three minutes while performing a number recall task. This will help us measure your craving for opioids and cigarettes more accurately than just doing the scales. At the end of day two, we will obtain an MRI brain scan.

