The most commonly reported side effect of rTMS is headache. This headache is typically of a muscle-tension type. It usually develops during or immediately after the stimulation and may last for minutes to hours following the end of the stimulation. It is typically limited to the day of stimulation, and usually responds promptly to single doses of over the counter pain medications. Neck pain or scalp pain may also occur. Both are usually managed easily with over-the-counter analgesics.

As noted in Rossi et al. (2009), Loo and colleagues reported mild and transient changes in auditory threshold in two depressed patients following a 2-4 week rTMS course of rTMS (16). Cases of tinnitus have been reported after rTMS treatments. In addition, recently in a study investigating the effects of rTMS on symptoms of depression, a patient experienced moderate to severe tinnitus after an rTMS session in which earplugs were not used. Rossi et al. recommended that hearing protection always should be worn during rTMS application, and that individuals with cochlear implants not receive rTMS. In the current study, earplugs will be worn by all subjects during rTMS procedures. Individuals with cochlear implants will be excluded from participation.

Risks to the unborn children of pregnant women receiving rTMS are unknown. Pregnant women will be excluded in this study. If sexually active, the subject must agree to use appropriate contraceptive measures for the duration of the study. Medically acceptable contraceptives include: (1) surgical sterilization (such as a tubal ligation or hysterectomy), (2) approved hormonal contraceptives (such as birth control pills, patches, implants or injections), (3) barrier methods (such as a condom or diaphragm) used with spermicide, or (4) an intrauterine device (IUD). Contraceptive measures such as Plan B (TM), sold for emergency use after unprotected sex, are not acceptable methods for routine use. If the subject has any uncertainty about whether they could be pregnant, another urine pregnancy test will be performed before they can participate in this protocol.

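### After day one, no unconditional pregnancy test is required before stimulation: the only timed test is tied to an MRI that, on stimulation days, follows all four sessions

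*Combined protocol and SAP*

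**What the plan says.** The reason for the exclusion is given under Potential Risks & Benefits: "Risks to the unborn children of pregnant women receiving rTMS are unknown. Pregnant women will be excluded in this study". Pregnancy testing then appears in three places in the visible text.

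- **Study Population, exclusion criteria.** A positive test excludes a woman. No visit or time is attached to the test.
- **Potential Risks & Benefits.** A further test is conditional: "If the subject has any uncertainty about whether they could be pregnant, another urine pregnancy test will be performed before they can participate". The same paragraph adds contraception: "If sexually active, the subject must agree to use appropriate contraceptive measures for the duration of the study".
- **Digital Data, in the paragraph on MRI risk.** The unconditional, timed rule is "Women of child-bearing capacity will be evaluated for pregnancy using a urine pregnancy test prior to scanning".

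Research Procedures sets the order on stimulation days. "Subjects will receive all four sessions of either TBS or sham on one particular day", and then "At the end of the stimulation sessions and tasks, post session MRI brain scans will be collected". For day two the text repeats this: "At the end of day two, we will obtain an MRI brain scan". On day one, motor threshold is measured first and the baseline MRI comes after it. For detailed timing the section relies on attachments: "The figures also indicate the timing of these tasks". Digital Data also has urine collected before each TMS session, with drug screening as the only stated purpose.

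**The concern.** The hazard that motivates the exclusion is magnetic stimulation, but the one test that applies to every woman of child-bearing capacity and has a stated time is anchored to the MRI, a procedure the plan itself classes as minimal risk. On stimulation days that anchor sits at the wrong end of the visit.

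At stake is the group the exclusion is meant to protect. A woman who is unaware of a pregnancy has no uncertainty to report, so the conditional retest does not reach her. If the pregnancy became detectable after her last required test, she could receive a full day of active TBS before any further test was due. This is a participant-safety matter. It touches no endpoint or analysis.

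**Working it through.** The plan states no figure on this point, so the check consists of setting the testing rule against the visit order and then counting.

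**Step 1. What a scan-linked test guarantees at each visit** (order from Study Design and Research Procedures)

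| Visit | Order of events | A test done just before the scan would follow |
|---|---|---|
| Day one | baseline assessments, motor-threshold pulses, MRI | the motor-threshold pulses, but no TBS or sham session |
| Day two | four sessions with tasks, MRI | all four sessions |
| Day three, if a stimulation day | four sessions with tasks, MRI | all four sessions |

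The rule sets a latest time only. Staff may test in the morning, and nothing forbids it, but nothing in the visible text requires it either.

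**Step 2. Last required test before active TBS**

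- Scan-linked test done once, at the baseline MRI: the last required test is on day one, whichever day is active.
- Scan-linked test repeated at every MRI, active TBS on day two: the last required test that must precede the sessions is again the day-one test.
- Repeated at every MRI, active TBS on day three: it is the day-two test.

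In none of these cases must the test fall on the active day before stimulation. In all of them, some test precedes the first TBS or sham session.

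**Step 3. Number of exposed days per woman**

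- Crossover reading (Study Design; Research Procedures, with stimulation on days two and three): 2 stimulation days − 1 sham day = 1 active day.
- Single stimulation day (the reading that fits the modified amounts under Payment): 0 if sham, 1 if active.
- Maximum: 1. The plan describes sham as delivering no electricity to the brain, so sham days are not counted.

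**Step 4. Probability of an undetected pregnancy on the active day.** This depends on the number of days since the last test. The visible text labels the visits day one, two and three but gives no interval, so no figure can be calculated.

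**Step 5. Subjects actually affected.** The Continuation Review records 4 enrolled, all in the row and column for White cisgender men, and states that enrolment is closed. Affected: 0 of 4.

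**The case against.** The strongest objection is that protection is already layered. A positive test excludes at entry. The word *another* in the conditional rule implies that a routine test came first. Contraception is required for the length of the study. The day-one baseline MRI puts a scan-linked test ahead of every TBS or sham session. All of this stands. A reader might infer from the MRI anchor that a woman could receive TBS with no prior test at all, and the documents do not support that reading. What the layers leave open is a pregnancy that becomes detectable between the last required test and the active day.

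Second, the timeline figures that Research Procedures relies on are attachments outside the available text, and they are the natural place to schedule a visit-level test. It would be wrong to say that the plan lacks such a test. It can only be said that the visible text does not require one.

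Third, a reader might infer that the day-one motor-threshold pulses are given to untested women. That does not follow: the entry test has no stated time and may well come before them, and the plan's statement of unknown fetal risk concerns rTMS, not threshold pulses. They matter here only because a scan-linked test may legitimately come after them.

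Fourth, nobody enrolled is affected and no analysis changes. That is correct, and it limits the point to an optional improvement. It still has some value: eligibility admits women aged 18 to 60, Beyond Birth Clinic is one of the recruiting clinics, and the pilot is meant to support a resubmitted grant application, so the same rule could carry over into later work.

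**Conclusion.** The point holds in a narrow form. On the visible text, a test should precede all TBS or sham sessions, but no unconditional test is required before stimulation on a stimulation day, the age of the previous result is not bounded, and the day-one test may follow the motor-threshold pulses.

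The size is at most 1 active-TBS day per woman, with no probability attached, and 0 of the 4 enrolled subjects. The conclusion assumes that the timeline attachments do not already schedule an earlier test; if they do, only the wording of the main text needs aligning. It does not depend on whether day three is still a stimulation day, because day two alone is enough. No harm to any participant is shown or implied. This is a cheap improvement that could be made.

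**What to change.** For women of child-bearing capacity, require a negative urine pregnancy test before the first TMS pulse at every visit that includes TMS: before motor threshold on day one, and before the first session on each stimulation day. On stimulation days, use the urine already collected before TMS. Let the result serve as that day's pre-scan test.

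Apply the rule at active and sham visits alike. The principal investigator and the subjects are blind to assignment, and testing on active days only would reveal it.

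Cost: on day one the pre-scan test is only moved earlier, so no strip is added. On stimulation days the addition is 0 strips per visit if the test is already repeated at each scan, otherwise 1. Over 1 or 2 stimulation visits this gives (0 or 1) × (1 or 2) = 0 to 2 extra strips per woman. No extra visit is needed, and no extra urine sample on stimulation days. If the timeline attachments already contain this timing, one sentence in the main text is enough.
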